Participant discontinues study intervention after Week 48 and up to Week 248	X	X	The video ileocolonoscopy at the SID visit is optional for participants who discontinue after Week 48 and before Week 96, since these participants would have completed the procedure as part of the Week 48 visit. Discontinuation at Week 96: A video ileocolonoscopy (with biopsy samples) is required at the Week 96 visit (or can be performed as part of SID visit if the SID visit occurs at Week 96). Note: Upon study unblinding (after Week 48 DBL), placebo participants who have not been rescued with guselkumab will be discontinued from study intervention and will have only an FES follow-up visit.
Participant completes the 248-week study		X	The FES follow-up visit should occur approximately 12 weeks after the last study intervention administration.

Footnotes:

Status: Approved, Date: 04 October 2024

Abbreviations: DBL=database lock; FES=final efficacy and safety; SID=study intervention discontinuation (visit)

a. The SID visit should be completed at the time of SID.

b. The FES follow-up visit should be completed approximately 12 weeks after the last dose of study intervention.

(b) Evaluations to be completed at the SID or FES visits are outlined below

b) Evaluations to be completed at the SID or FES visits			
Period:	SID	FES	
Study Procedures			Notes:
Safety Assessments			
Physical examination	X	X	A targeted physical examination will be performed (see Section 8.2.1).
Vital signs	X	X	Include: temperature, pulse/heart rate, respiratory rate, and blood pressure
Urine pregnancy test	X	X	Must be performed in female participants of childbearing potential.
TB evaluation/other infection assessment	X	X	If TB is suspected at any time, study intervention should be withheld and an immediate and thorough investigation should be undertaken. More information on TB evaluation is provided in Section 8.2.10.
C-SSRS	X	X	The C-SSRS should be completed after all PRO assessments and before any other tests, procedures, or other consultations to prevent influencing participant perceptions. The investigator or trained study site personnel will interview the participant and complete the C-SSRS.
Efficacy Assessments			

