Collect and review Symptom and Health Diary CDAI BSFS AP-NRS	Xa Xa Xa	Xb	For the FES follow-up visit, daily diary information should be collected for at least 14 days before the visit. The daily diary includes patient-reported data for the CDAI. The most recent hematocrit value obtained will be used to calculate the CDAI. Collection of daily diary information will conclude at Week 108/FES visit (if the FES visit occurs prior to Week 108).
			Collection of BSFS and AP-NRS will conclude at Week 48/the SID visit (if the SID visit occurs prior to Week 48).
Weight	Xª	Xb	Weight measurement is used to support CDAI assessments, PK modeling, and safety.
Fistula assessment	Xª		
Video ileocolonoscopy	Xª	X ^{#,b}	See notes in Table 5 (a). Ileocolonoscopy is not required at the FES follow-up visit. # However, if the SID visit occurs prior to the Week 8 time point, video ileocolonoscopy should be done at the FES follow-up visit instead of the SID visit.
Stool sample (fecal calprotectin)	Xª	X#,b	Stool samples required for this visit must be obtained (through on-site or at-home collection) before the start of the bowel preparation for the video ileocolonoscopy that is also scheduled for the visit. See notes in Table 5 (a). Stool sample is not required at the FES follow-up visit. # However, if the SID visit occurs prior to the Week 8 time point, stool sample should be done at the FES follow-up visit instead of the SID visit.
CRP	Xª	X ^b	
Patient-reported Outcomes			
IBDQ	Xª		PRO assessments for efficacy. IBDQ and PROMIS-29 should be administered before the C-SSRS and before
PROMIS-29	Xa		any clinical procedures or tests are performed.
Clinical Laboratory Assessments	·		
Hematology and chemistry	X	X	For SID visit that occurs after Week 96, only the chemistry laboratory assessments should be performed. For FES visit that occurs after Week 108, only the chemistry laboratory assessments should be performed.

Period:	SID	FES	
Study Procedures			Notes:
Pharmacokinetics/Immunogenicity			
Study intervention serum concentration	Xª	Xb	All reasonable attempts should be made to collect samples at the scheduled time points and record the actual times of PK sample collections.
Assessment for antibody to study intervention	Xª	Xb	All reasonable attempts should be made to collect samples at the scheduled time points and record the actual times of sample collections.
Pharmacodynamics and Biomarkers			

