At Week 24, all participants will enter the extension phase and receive the same treatment regimen that they were receiving at Week 24. Database locks are planned for Week 24, Week 48, and when the last participant completes the last scheduled assessment. Additional DBLs may be added as necessary.

The co-primary endpoints of this study are clinical remission at Week 12 and endoscopic response at Week 12 (refer to Section 5.3 for endpoint definitions and analyses). Additionally, there are 3 secondary endpoints in the study (refer to Section 5.4 for definitions and analyses methods). The primary and secondary endpoints will be analyzed at the first DBL, which occurs at Week 24 DBL. Only data through Week 24 will be included in the Week 24 DBL for analyses.

The study will be unblinded to investigators and participants after the last participant completes the Week 48 evaluations and the Week 48 database lock (DBL) is completed. Upon study unblinding, placebo participants who have not been rescued with guselkumab will be discontinued from study intervention and have a final efficacy and safety (FES) visit. All other participants will continue on guselkumab treatment through Week 96.

In general, participants who are receiving oral 5-aminosalicylic acid (5-ASA) compounds, oral corticosteroids, conventional immunomodulators (AZA, 6-MP, or MTX), antibiotics, and/or enteral nutrition for the treatment of Crohn's disease at baseline should maintain a stable dose for the specified period before baseline, and through Week 48, with the exception of oral corticosteroids. Starting at Week 12, all participants who were taking corticosteroids at Week 0 must begin tapering their corticosteroid dose. This tapering is mandatory, unless not medically feasible.

From Week 0 through Week 48, enrolled participants should not initiate any of the following concomitant Crohn's disease-specific medical therapies:

- Oral or rectal 5-ASA compounds
- Immunomodulators (ie, AZA, 6-MP, or MTX)
- Oral, parenteral, or rectal corticosteroids, including budesonide and beclomethasone dipropionate
- Antibiotics as a primary treatment for Crohn's disease
- Total parenteral nutrition or enteral nutrition as a treatment for Crohn's disease

Details regarding the prohibited changes in concomitant Crohn's disease-specific medications for participants are included in Section 6.2 Appendix 2.

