5.1.1. Visit Windows

Unless otherwise specified, nominal scheduled visits (described in SoA of the protocol) will be used for over time summaries and listings with no visit windows applied. However, the Unscheduled Visit (USV), Study Intervention Discontinuation (SID) and Final Efficacy and Safety (FES) visits will be slotted to scheduled visits according to the following mapping rules except for SES-CD endpoint:

- 1. Assign a visit number to USV, SID or FES visit based on the Study Day as illustrated in Table 2
- 2. If USV, SID or FES visit falls in the window of a scheduled visit and there are not already data for the scheduled visit, assign the scheduled visit number to the USV, SID or FES visit. If there are already data for a same scheduled visit, those data will be used in lieu of the USV, SID or FES visit data.

Week 4	Day 2-42
Week 8	Day 43-70
Week 12	Day 71-98
Week 16	Day 99-126
Week 20	Day 127-154
Week 24	Day 155-182
Week 28	Day 183-210
Week 32	Day 211-238
Week 36	Day 239-266
Week 40	Day 267-294
Week 44	Day 295-322
Week 48	Day 323-350
Week 52	Day 351-378
etc.	
Week 96	Day 659-686

Table 2: SID/FES/Unscheduled Visit Slotting

More frequent measurements are taken for other endpoints compared to endoscopic assessments taken only at Weeks 0, 12, 48, and 96.

For SES-CD endpoint using a wider window: +/- 4 weeks

Week 12: Days 57 to 113

Week 48: Days 309 to 365

Week 96: Days 645 to 701

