5.4.2. Estimands

5.4.2.1. Estimands for the Secondary Endpoints

Secondary Estimand of Clinical Remission at Week 24 (Main Estimand 5)

The following describes the attributes of the Main Estimand 5.

Treatment by Week 24:

Experimental:

- Guselkumab ^{CCI} q4w (Weeks 0, 4, and 8) followed by guselkumab ^{CCI} q4w (Weeks 12, 16, and 20)
- Guselkumab ^{CCI} q4w (Weeks 0, 4, and 8) followed by guselkumab ^{CCI} q8w starting at Week 16

Control: Placebo SC q4w (Weeks 0, 4, 8, 12, 16, and 20)

Population: Participants with moderately to severely active Crohn's disease

Variable (Endpoint):

A binary response variable (response/nonresponse) where response is defined as achieving CDAI score <150 at Week 24 without experiencing any of the ICEs in categories 1, 2, 3, 5 and 6 as outlined below prior to the Week 24 visit.

Intercurrent events and corresponding strategies:

ICE Identifier	ICE Description	Corresponding Strategy
1	A Crohn's disease-related surgery (with the exception of minor procedures such as drainage of a superficial abscess or seton placement, etc.)	Composite
2	A prohibited change in Crohn's disease medication (See Appendix 2)	Composite
3	Discontinuation of study intervention due to lack of efficacy or an AE of worsening of Crohn's Disease	Composite
4	Discontinuation of study intervention due to COVID-19 related reasons (excluding COVID-19 infection) or regional crisis	Treatment Policy
5	Discontinuation of study intervention due to COVID-19 infection or for reasons other than those specified in ICE categories 3 and 4	Composite
6	Meets rescue criteria as determined by the IWRS	Composite

The composite strategy assesses the treatment effects not only based on the variable measurements, but also based on ICEs. This estimand acknowledges that having an ICE in categories 1-3, 5 and 6 is an unfavorable outcome. For participants experiencing ICE category 4, the treatment policy strategy considers the occurrence of ICE category 4 is irrelevant in defining the treatment effect.

Population-level summary:

Difference in proportions of responders (according to the **Variable** defined above) between each guselkumab group and the placebo group.

Secondary Estimand of PRO-2 Remission at Week 12 (Main Estimand 6)

The same estimand (except for the "Variable" attribute) that is specified for the co-primary endpoint analyses will be used.

Variable (Endpoint):

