Similar methodology used for analyzing endpoints through Week 24 will be applied to the endpoints analyses after Week 24. Specifically, the estimand approach and analysis methods specified in Sections 5.4.2.1 and Section 5.4.3.1 for the secondary endpoints will apply to the two exploratory binary endpoints (clinical remission at Week 48, endoscopic response at Week 48). Unless otherwise specified, the ICEs are the same as those specified in Sections 5.4.2.1.

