6.2. Appendix 2 Prohibited Changes in CD Medications (Intercurrent Event 2)

(1) **Prohibited medications**

Initiation of the following prohibited medications after Week 0

- a. Immunomodulatory agents other than AZA, 6-MP, or MTX (including, but not limited to, 6-thioguanine, cyclosporine, mycophenolate mofetil, tacrolimus, and sirolimus).
- Immunomodulatory biologic agents (including, but not limited to, TNFα antagonists, natalizumab, ustekinumab, rituximab, vedolizumab).
- c. Experimental Crohn's disease medications (including, but not limited to, upadacitinib, filgotinib, ozanimod, etrolizumab, brazikumab, mirikizumab, risankizumab, and andecaliximab).
- d. Thalidomide or related agents.

(2) Corticosteroids

The occurrence of the following changes in corticosteroid usage during induction treatment (ie, before week 12), OR, between week 36 and week 48, including changes initiated before week 36 and continued after week 36, unless otherwise specified.

- a. Initiation of oral corticosteroids (including budesonide and beclomethasone dipropionate), parenteral, or rectal corticosteroids due to worsening Crohn's disease.
- b. Increase in the dose of oral corticosteroids (including budesonide and beclomethasone dipropionate), as specified below, above the baseline dose due to worsening Crohn's disease.
 - i. Oral corticosteroids > 5 mg/day (prednisone equivalent)
 - ii. Oral budesonide > 3 mg/day
 - iii. Oral beclomethasone dipropionate > 5 mg/day
- c. Initiation of oral corticosteroids (including budesonide and beclomethasone dipropionate) due to reasons other than worsening Crohn's disease for more than 7 days during induction treatment, OR, for more than 28 days during maintenance treatment.
- d. Increase in the dose of oral corticosteroids (including budesonide and beclomethasone dipropionate), as specified below, above the baseline dose due to reasons other than worsening Crohn's disease for more than 7 days during induction treatment, OR, for more than 28 days during maintenance treatment.
 - i. Oral corticosteroids > 5 mg/day (prednisone equivalent)
 - ii. Oral budesonide > 3 mg/day
 - iii. Oral beclomethasone dipropionate > 5 mg/day

(3) Immunomodulator agents

- a. Initiation of oral 6-MP/AZA due to worsening Crohn's disease.
- b. Initiation of oral, subcutaneous, or intramuscular MTX due to worsening Crohn's disease.
- c. Increase in the dose of oral 6-MP/AZA above the baseline dose due to worsening Crohn's disease.

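### After unblinding, the SAP's discontinuation rule scores the mandated stop of unrescued placebo participants as non-response, which biases any later placebo comparison toward guselkumab, most at Week 96

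*SAP*

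**What the plan says.** SAP 5.5.3, under After Week 24, states: "Similar methodology used for analyzing endpoints through Week 24 will be applied to the endpoints analyses after Week 24". It adds: "Unless otherwise specified, the ICEs are the same as those specified in Sections 5.4.2.1". The section it points to, SAP 5.4.2.1, gives ICE 5 the composite strategy and defines it as "Discontinuation of study intervention due to COVID-19 infection or for reasons other than those specified in ICE categories 3 and 4". ICE 6, meeting the rescue criteria, is also composite.

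On conduct, SAP 1.2 says: "Upon study unblinding, placebo participants who have not been rescued with guselkumab will be discontinued from study intervention". Protocol 1.3, Table 5(a), says that these "placebo participants who have not been rescued with guselkumab will be discontinued from study intervention and will have only an FES follow-up visit". Everyone else continues guselkumab.

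On data after the stop, SAP 5.1.1 says that unscheduled, discontinuation and "Final Efficacy and Safety (FES) visits will be slotted to scheduled visits according to the following mapping rules except for SES-CD endpoint", and only where the scheduled visit is empty. For endoscopy, protocol Table 5(b) says: "Ileocolonoscopy is not required at the FES follow-up visit". The one exception there concerns stops before Week 8.

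Missing data count as non-response for CDAI and PRO-2 endpoints (SAP 5.4.3.1) and for binary histology (SAP 5.5.3). For a missing SES-CD, the SAP states such a rule only at Week 12 (5.3.3.1).

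**The concern.** The stop at unblinding is an administrative decision applied to one arm. It says nothing about how the participant was doing. ICE 5 is a catch-all, so the stop is nevertheless scored as treatment failure. Any placebo comparison at a later visit would then partly measure how many placebo participants had reached that visit before unblinding, which is a matter of the accrual calendar. Week 96 is the most exposed efficacy visit and has its own planned database lock. At stake are the Week 96 differences from placebo and their nominal p-values.

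**Working it through.** **1. Which category the stop falls in.** ICE 3 is lack of efficacy or worsening Crohn's disease. ICE 4 is COVID-19 logistics or regional crisis. The mandated stop is neither, so by its wording it is ICE 5. The SAP can limit an ICE in time when it wants to: the corticosteroid rule in Appendix 2 applies before Week 12 or "between week 36 and week 48, including changes initiated before week 36 and continued after week 36". ICE 5 has no such limit, and SAP 5.7.4 still counts it as unfavourable in analyses that extend to Week 96.

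**2. Which visits are affected.** Unblinding follows the last participant's Week 48 visit and the Week 48 lock. Every Week 48 and earlier result is therefore complete beforehand.

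**3. Whether placebo comparisons are planned later.** Protocol 3 bases endpoints after Week 12 on each guselkumab group against placebo. Protocol 9.4.4 evaluates tertiary endpoints through Week 96. SAP 5.5.2.5 lists binary endoscopic endpoints at Week 96, and SAP 5.5.3 promises nominal p-values for the other exploratory endpoints. Nothing ends placebo comparisons at Week 48.

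**4. The plan's own figures.** A pooled-variance normal approximation with 106 placebo v 212 guselkumab, two-sided 0.05, gives above 99.9% for 15% v 45%, 50% and 55%. It gives 91.4% for 10% v 25%, 93.9% for 13% v 30% and 99.4% for 13% v 35%. SAP Table 1 states >99%, 91%, 94% and >99%, so it is reproduced. The documents give no Week 96 figure.

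**5. Share converted.** Assumed, not in the documents: uniform accrual over A weeks, lag L from the last Week 48 visit to unblinding, and response unrelated to entry date. The share of placebo participants unblinded before their own Week W is f = (W − 48 − L)/A, held between 0 and 1.

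| Visit | A=104, L=14 | A=52, L=6 |
|---|---|---|
| Week 52 | 0% | 0% |
| Week 56 | 0% | 2/52 = 4% |
| Week 64 | 2/104 = 2% | 10/52 = 19% |
| Week 80 | 18/104 = 17% | 26/52 = 50% |
| Week 96 | 34/104 = 33% | 42/52 = 81% |

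Other inputs move these shares: with A from 26 to 104 and L from 0 to 8, the Week 96 share runs from 38% to 100%.

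**6. Effect on the difference.** The artificial part is p × f, with p the placebo rate. The plan's Week 12 rates are borrowed for Week 96 as a further assumption:
- 30% v 13%: 30 − 13(1 − f) = 21.25 to 27.5 points instead of 17.
- 50% v 15%: 50 − 15(1 − f) = 39.9 to 47.1 points instead of 35.

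The next figures are the exact probability that an unstratified two-sided 5% chi-square test, 106 v 106, favours guselkumab. It stands in for the stratified test. For 30% v 13% it rises from 87% to 98% or more; for 50% v 15% it is near 100% throughout. With no true difference:

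| Rate in both arms | Artificial difference (points) | Probability of favouring guselkumab | Same, with f = 0 |
|---|---|---|---|
| 5% | 1.6 to 4.0 | 7% to 40% | 2.2% |
| 13% | 4.25 to 10.5 | 17% to 86% | 2.6% |
| 15% | 4.9 to 12.1 | 19% to 91% | 2.6% |

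**7. Amending ICE 5 only.** The follow-up visit falls about 12 weeks after the last dose. It lands in the Week 96 window (Days 659 to 686) only if the last dose was at Week 84, that is, if unblinding fell in the participant's Weeks 84 to 88. That share is 4/A, or 4/104 = 4% to 4/52 = 8%. Non-responder imputation would still convert (34 − 4)/104 = 29% to (42 − 4)/52 = 73% for CDAI and PRO-2 endpoints. For binary histology the share stays at 33% to 81%. For SES-CD it also stays there if the Week 12 rule is extended, which is likely but not written.

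**The case against.** The strongest reply is that no sentence announces a Week 96 test against placebo. The sentence in SAP 5.5.3 beginning with Specifically names only the two Week 48 endpoints, the general wording promises similar rather than identical methods, and the protocol speaks of applicable timepoints. This stands as a limit on certainty: the comparison is inferred from general wording. It does not remove the problem, because that wording covers later endpoints and nothing excludes them.

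A second reply is that ICE 5 is not the main cause: placebo follow-up ends by design, so the data would be missing anyway. This is largely right, as step 7 shows, and it is why the fix must cover both routes. The protocol's own treatment-policy handling of ICE 5 (9.4.2, 9.4.3) would meet the same missing-data problem.

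Third, the results concerned are exploratory and nominal, and the disposition tables will show the reasons for stopping before Week 92. That limits the severity.

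A reader might also infer that no placebo participant at all can respond after unblinding. That is slightly too absolute: someone stopped under ICE 4 shortly before unblinding falls under treatment policy, and follow-up data may be slotted to an empty visit.

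**Conclusion.** The point holds for binary endpoints at visits after unblinding. Followed as written, the SAP scores essentially all such placebo visits as non-response, and the bias runs toward guselkumab. It cannot shrink as the visit week rises, so it is largest at Week 96. The Week 96 figures (33% to 81% converted, 1.6 to 12.1 artificial points at placebo rates of 5% to 15%) rest on assumed accrual and lock timing; they are illustrations, not bounds.

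Two stronger readings are not supported. One is that the trial's main conclusions are compromised: the co-primary, secondary and Hochberg-tested Week 48 results all precede unblinding. The other is that continuous endpoints are also biased toward guselkumab. SAP 5.5.3 assigns them baseline values after ICE 5, which favours guselkumab where the stopped participant was better than baseline and placebo where worse, so no direction or size can be claimed. Severity: minor to should-fix.

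**What to change.** In SAP 5.5.3:
1. Exclude from ICE 5 the protocol-mandated discontinuation of placebo at study unblinding.
2. Treat those participants' visits after unblinding, including slotted follow-up data, as not applicable, rather than as non-response or baseline values.
3. Give no guselkumab-versus-placebo p-values for visits after Week 48, and summarise those visits descriptively for the two randomised guselkumab groups.
4. If the placebo-to-guselkumab group defined for safety in SAP 5.6 is also summarised for efficacy, state that ICE 6 is handled there by treatment policy, as SAP 5.7.2 and 5.7.4 already do. Otherwise every member fails by rule and the group shows 0% response.

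The cost is SAP wording, with no change to conduct or data collection. Nominal placebo p-values are lost at early visits that are little affected: 0% converted at Week 52 and 0% to 4% at Week 56 under the assumptions above.

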5.6. Safety Analyses

Safety analyses will be based on the Safety Analysis Set, unless otherwise specified. In general, participants will be analyzed according to their assigned treatment. However, participants assigned to placebo who incorrectly received guselkumab at any time will be analyzed in the guselkumab group from the time they received guselkumab.

For all continuous safety variables, descriptive statistics by intervention group will include the N, mean, standard deviation, median, minimum, and maximum. Categorical variables will be summarized by intervention group using frequency counts and percentages. No formal statistical comparisons are planned.

Safety data, including but not limited to, AEs and changes in laboratory assessments, will be summarized. Treatment-emergent AEs will be summarized by intervention group and Medical Dictionary for Regulatory Activities (MedDRA) system organ class and preferred terms.

Safety data will be summarized through Weeks 12, 24, 48, and the end of the study.

- Safety data limited to the induction period (ie, through Week 12) will be summarized by treatment groups (columns):
 - 1. Placebo
 - 2. Guselkumab^{CCI} \rightarrow ^{CCI} q8w 3. Guselkumab^{CCI} \rightarrow ^{CCI} q4w
 - 4. Guselkumab Combined (columns 2-3)
- Safety data through Weeks 24, 48, and the end of the study will be summarized with the following groups (columns):

1. Placebo (include all placebo participants excluding data after a participant was rescued with guselkumab)

2. Placebo \rightarrow Guselkumab (include placebo participants who were rescued with guselkumab; data in this group occurred after a subject crossed over to guselkumab).

q4w

3. Guselkumab \bigcirc CCl \rightarrow \bigcirc Q8w

→ CCI

- 4. Guselkumab CCI
- 5. Guselkumab Combined (columns 3-4)
- 6. All Guselkumab (columns 2-4)

